This proposal unites neuroimagers, experts in conducting and analyzing human PET studies with behavioral scientists, experts in developing and testing treatments for alcoholism. We will conduct the first-ever *in vivo* PET imaging study of KOR and NTX occupancy in two cohorts of HD (18 FHP and 18 FHN) and relate our imaging findings to FH and alterations of drinking behavior by NTX in the ADP. Through this work, we will advance our understanding of (a) the degree of involvement of the kappa system in reducing drinking in humans by NTX, (b) the contribution of FH to this relationship, and (c) refine the use of a new PET imaging tracer. In so doing, we will inform the development of future targeted pharmacotherapies for alcoholism and lay the groundwork for other important investigations into the KOR/dynorphin system *in vivo*.

Primary (P), Secondary (S), and Auxiliary (A) Specific Aims:

- P1. **Occupancy of KOR by NTX and drinking:** To determine the degree to which occupancy of KORs by a 100 mg/day dose of NTX mediates (influences the strength of) responsivity to NTX treatment in all heavy drinkers. It is expected that KOR occupancy will significantly mediate the relationship between NTX treatment and responsivity. „Responsivity“, measured via ADP, is the change in number of drinks consumed at the baseline ADP vs. NTX ADP.
- P2. **Family History of Alcoholism as a moderator:** To determine whether the relationship between NTX responsivity and occupancy of KOR is different in FHP vs. FHN heavy drinkers.
- P3. To determine if baseline KOR availability differs between heavy drinkers and healthy control socialdrinkers

S1. **Baseline KOR differences**

- a. To determine if baseline levels of KOR differ between FHP and FHN heavy drinkers.
- b. To determine if baseline KOR level is related to either baseline drinking or responsivity to NTX.

S2. **Identify and validate a reference region** (area devoid of specific binding) for our new KOR tracer. A reference region would simplify PET analysis.

S3. **Optimize the scan duration** for clinical populations being imaged with the new KOR tracer.

Shorter scans would increase compliance and decrease discomfort to subjects.

A1. **Relationship to other behavioral measures:** To determine if occupancy of KORs is related to measures of alcohol craving, stimulation or sedation, assessed in the ADP.

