Mock PET scan: As time and scheduling permits, we will conduct a mock PET scan prior to the baseline PET and ADP. During the mock PET session, the subject will lie in a replica of the PET scanner, be told when the scanner is being "turned on" and when blood samples are "being drawn".

Medication Administration: Eligible participants will receive NTX for a five to eleven day period. The dose of NTX will be tapered up over the first four days as shown in figure 9 above. Participants will come into our clinic on a daily basis to take their medications and provide reports on drinking behavior and adverse events. In the event that a participant cannot come to the clinic daily, other arrangements will be made, such as giving the participant more than one dose of their medication at a time and using a daily phone call as both a reminder to take the medication and as a means to monitor adverse events. We will allow this up until the final two doses of medication prior to the ADP or PET. This arrangement will be determined by the investigator and her staff based on the participant's other obligations and compliance. Healthy controls will not take any medication.

Alcohol Drinking Paradigm: The procedures for all the alcohol-drinking sessions will be similar. Participants will be told not to consume alcohol starting at 5 pm the night before and arrive at the Hospital Research Unit (HRU) of Yale New Haven Hospital, New Haven, at 9:00 am. We will first assess breath alcohol levels and conduct urine drug tests. If the urine drug tests are positive and/or breath alcohol levels are 0.05 or greater, then the session will be rescheduled. Participants will be given the opportunity to taste and drink two chosen beverages (of which they will choose one for the 2 ADPs; see below). These procedures will make them more comfortable drinking in the HRU room and will also help reduce order effects in the current design.

The ADP will be conducted in a private room in the HRU. It will start at 3 pm with the priming dose period, which will be followed by three one-hour drinking periods (4-5 pm, 5-6 pm, and 6-7 pm), and will conclude at 7 pm.

Exposure to Alcohol Cue

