Analysis of Initial Cohort: Data from the first 6 FHP and 6 FHN subjects scanned in year one of the project (24 scans total) will be analyzed to determine whether or not a reference region exists for [11C]LY2795050 ([11C]-PKAB) and whether or not the scan duration can be shortened without loss of precision of the data. To be sure that a reference tissue model is appropriate in our study, two findings are required. The V_T of the putative reference region must be unchanged by blocking and the endpoint, BP_{ND} , estimated by the reference region method must agree with the BP_{ND} calculated using an AIF. If the BP_{ND} values from 2T and SRTM continue to show excellent agreement, as applied to *both* baseline and NTX scans, then we may choose to discontinue arterial sampling thereafter and rely solely on a reference region model for analysis. After a preliminary analysis of the initial cohort, we will determine the acquisition protocol for the remaining 24 subjects.

Modeling of PET data to yield BP in regions of interest and parametric images

1. Standard kinetic modeling approaches: With plasma input function measurements in hand, we can compare multiple standard methods of estimating our desired endpoints (BP_{ND} at baseline and difference in BP_{ND} from baseline to NTX) to determine the best model or technique [52] that yields the lowest variance in the estimates. Tentatively based on preliminary data, we expect to use the cerebellum as the reference region for reference region methods but we will continue to investigate the possibility of another (better) reference region.

2. Measuring occupancy does not depend on displacement, time of day:

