The two primary imaging endpoints (B_{avail} and $Occup^{Kappa}$) depend on our ability to measure BP_{ND} . It is important to note that the half-life of NTX is very long (10.5 hrs in the blood at 100 mg oral dose) and subjects would have been on 100 mg for at least 2 days before the NTX scan. Therefore, we can expect that NTX in the brain will be at a nearly constant level prior to and during the NTX-scan. Thus, we are not measuring displacement of [11C]LY2795050 ([11C]-PKAB) but rather, the effect of a pre-blocking (i.e., a measurement at a second steady state). This is an important distinction. The latter does not depend on the displaceability of the tracer (a kinetic issue), and thus, we have not addressed it in our preliminary data. To be safe, however, we will scan each subject near mid-day for both baseline and NTX scans. Given that the half-life of NTX is 10.5 hours and that it drops ~5% per hour, we will maintain the delay from morning oral dose of NTX to time of scan for each subject at 2 hours which should coincide with the time of peak NTX concentration in the blood.

Assessments

- a) Socio-demographic/General Information: At intake, demographic data, medical history, and family psychiatric history will be assessed with interviews and self-report forms that provide data on age, race, socioeconomic status, marital status, educational and occupational levels, and significant medical history. These are adapted from previous diagnostic and clinical studies at

this center.

- b) SCID: The Structured Clinical Interview for DSM-IV (SCID) [41] will be used to determine psychiatric diagnoses. This interview assesses DSM-IV current and lifetime psychiatric diagnoses for anxiety, mood, psychotic, alcohol and substance use, somatoform, and eating disorders.

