The preliminary data in this section represent our initial experience with the new PET tracer [^{11}C]LY2795050 ([C-11]-PKAB) in humans and monkeys. A number of opioid receptor radiotracers are currently available for PET imaging in humans: [^{11}C]carfentanil(μ -specific), [^{11}C]/[^{18}F]diprenorphine (nonspecific), [^{11}C]buprenorphine (nonspecific), [^{18}F]cyclofoxy (μ , κ), and [^{11}C]methylnaltrindole (δ) [33]. None of these existing tracers is selective for KOR. So far, the results with [^{11}C]LY2795050 ([C-11]-PKAB) suggest that it is taken up consistent with the known distribution of KOR [34-36]; It also appears to have good contrast to background properties, good test/retest reproducibility, and there may be a reference region with little to no KOR.

[figure not shown]

Figure 2. Top row: MRI images of an individual subject. Middle row: 0-10 min summed PET image. Bottom: 60-120 min summed PET image. Left column: axial slice; middle column: coronal slice; right column: sagittal slice. The amygdala is bright on all three views at late time. The cingulate cortex is apparent on the coronal image at late time.

Occupancy of KOR by NTX – or simply “occupancy” - is measured as a percentage change in BP_{ND} from the baseline condition to the drug condition (in our case, a week of NTX treatment). If we assume that neither the K_D nor the f_{ND} of the tracer change in an individual between scans, then occupancy can be seen to be the fractional change in available receptors due to the drug.

Total Volume of Distribution, V_T , is a related concept to BP. V_T is the equilibrium ratio of the concentration of parent tracer in tissue to parent tracer in plasma.

b. In vitro results

Radioligand competition assays were conducted to assess the *in vitro* binding affinities of LY2795050 to opioid receptors. LY2795050 is a KOR antagonist and displays high binding affinity and great selectivity to KOR *in vitro* ($K_i = 1.37, 87.3, \text{ and } 475 \text{ nM}$, respectively, for kappa, mu, and delta receptors) [38].

[figure not shown]
[figure not shown]
c. Test/retest imaging in humans

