region. However, the definitive identification of a reference region must be based on displacement experiments.

f. Regional distribution of desired endpoint: KOR at baseline (BP_{ND})

We computed BP_{ND} in each ROI two ways. One method requires the use of AIF and the other does not. From the fits of the TAC data via 2T model with AIF, we calculated BP_{ND} as the relative difference in volumes of distribution between the target ROI and the putative reference region, in this case, cerebellum: $(V_T(ROI) - V_T(CER)) / V_T(CER)$. BP_{ND} was also computed using the Simplified Reference Tissue Model (SRTM) using the cerebellum as the reference region. The regional distribution of BP_{ND} based on 2T and SRTM is shown in Figure 4. Figure 4 shows that the methods are in close agreement and the variability, by region, across the cohort is small.

[figure not shown]

Figure 5 **a.** Effect of pre-block with unlabeled KOR antagonist drug. Baseline TACs for cerebellum (CER), caudate (CAU), and frontal cortex (FRO) (solid circles, open circles, diamond, all in red). Curves after pre-block (blue) all show reduced specific binding and are nearly indistinguishable from CER at baseline. Curves are from one animal and are normalized to injected activity dose. **b.** BP_{ND} is reduced dose-dependently according to dose of specific KOR antagonist in both CAU and FRO region.

g. Pre-blocking of [11C]LY2795050 ([C-11]-PKAB): can we detect drug occupancy at kappa sites?

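### Primary aim P3 rests on equal reference-region uptake in heavy drinkers and controls, which the cerebellum validation does not test; stopping arterial sampling could discard the control data that would show a difference

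*Combined protocol and SAP*

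**What the plan says.** The Specific Aims list P3 as a primary aim: "To determine if baseline KOR availability differs between heavy drinkers and healthy control socialdrinkers". The Statistical Considerations have no paragraph for P3, so its measure has to be inferred. PET Methods (the item on measuring occupancy) makes both primary imaging endpoints, available receptors and occupancy, depend on BP_ND.

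Section VI item 2, part f, computes BP_ND from the two-tissue model with arterial input as "the relative difference in volumes of distribution between the target ROI and the putative reference region", namely the cerebellum. The simplified reference tissue model (SRTM) uses the same region.

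Under Analysis of Initial Cohort, the reference region is examined in the first 6 family-history-positive and 6 family-history-negative subjects, two scans each. Two findings are required: cerebellar V_T unchanged by naltrexone, and SRTM agreeing with the arterial-input estimate. If they hold, "then we may choose to discontinue arterial sampling thereafter and rely solely on a reference region model for analysis". The PET Methods paragraph on dispensing with arterial sampling goes further and would analyse all data with reference tissue models.

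The constancy assumption stated in Section VI item 2 is within-person: "If we assume that neither the K_D nor the f_{ND} of the tracer change in an individual between scans". On controls, Procedures says "Healthy controls will not take any medication". Section X item 2 shows that an arterial line is the default at their one PET scan.

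**The concern.** The two validation findings answer a within-person question. The first compares a subject with himself or herself under naltrexone; the second compares two methods on the same scan. Both suit occupancy, which is a change within one person. P3 compares different people in two groups, so it also needs the denominator of BP_ND to mean the same thing in each group.

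Neither finding can show that. Controls are not in the validation cohort and have no blocked scan. Agreement between the two-tissue model and SRTM is uninformative because both divide by the cerebellum. Section VI item 2, part h, itself says that this agreement does not validate the cerebellum and that both estimates could be biased.

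A group difference in the reference would move BP_ND in the same direction in every region and could pass for a consistent receptor effect, or hide a real one. Cerebellar V_T could reveal it, and V_T needs arterial data.

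**Working it through.** **The plan's own counts.** (6 + 6) × 2 = 24 scans, as stated, all from heavy drinkers. The acquisition decision is then said to cover the remaining 24 subjects. That is 36 − 12, from the 18 + 18 design in the aims section; the current target gives 56 − 12 = 44. Neither number includes controls, so the decision does not say what applies to them.

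**Inputs from the documents.** BP_ND = V_T(region)/V_T(cerebellum) − 1 (Section VI item 2, part f); 56 heavy drinkers and 10 controls (Targeted Enrollment; Section VII item 1 says 25 controls); two-sided alpha 0.05 (Statistical Considerations).

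**Assumptions.** Readable text gives no BP_ND level, no between-subject CV and no V_T by group. I take true BP_ND b = 0.5 or 1.0, a BP_ND CV of 20% (range 15–30%), and a cerebellar value in heavy drinkers of k = 0.95 times that in controls, with no receptor difference in the target regions.

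**Relative bias in BP_ND**

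- All V_T scale together (for example, a plasma free-fraction difference): the ratio is unchanged, so the bias is 0.
- Non-displaceable uptake shifts in every region, specific binding unchanged: BP_ND becomes b/k, and 1/0.95 − 1 = +5.3% for any b.
- Only the cerebellum shifts: BP_ND becomes (1 + b)/k − 1. For b = 0.5, 1.5/0.95 − 1 = 0.579, or +15.8%. For b = 1.0, 2/0.95 − 1 = 1.105, or +10.5%.

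**False-positive rate of P3.** Two-sample t test, non-central t, 64 df. Standardised shift d = bias/CV; non-centrality = d × √(56 × 10/66) = d × 2.913. For b = 0.5 with only the cerebellum shifted and CV 20%: d = 0.158/0.20 = 0.79, non-centrality 2.30.

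| Case, 5% lower in heavy drinkers | CV 15% | CV 20% | CV 30% |
|---|---|---|---|
| All V_T scale together | 5% | 5% | 5% |
| Non-displaceable uptake, all regions | 17% | 12% | 8% |
| Cerebellum only, BP_ND 1.0 | 52% | 33% | 17% |
| Cerebellum only, BP_ND 0.5 | 86% | 62% | 33% |

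With 25 controls and CV 20%, the last three rows become 19%, 58% and 90%.

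**How well V_T can check this.** The 95% half-width for the group difference in cerebellar V_T is t × CV × √(1/n₁ + 1/n₂). At an assumed V_T CV of 20%:

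- 56 versus 10: 1.998 × 0.20 × 0.343 = ±13.7%.
- 12 versus 10 (only the initial cohort has arterial data): 2.086 × 0.20 × 0.428 = ±17.9%.

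Power to detect a 5% difference is 11% and 9% respectively.

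**The case against.** The strongest reply has four parts.

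*BP_ND does not need equal cerebellar V_T.* A reader might infer that P3 requires it. It does not: a difference shared by all regions cancels in the ratio. This stands. The requirement is equal non-displaceable uptake, with cerebellar specific binding absent or equal.

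*Stopping arterial sampling does not cause the bias.* A reader might infer that it does. BP_ND from the two-tissue model has the same cerebellar denominator, so P3 is equally exposed with arterial lines in place. This stands too. What is lost is the means of seeing the problem.

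*The 62% is the extreme case.* Sampling stops only if naltrexone leaves cerebellar V_T unchanged, which makes it essentially non-displaceable uptake in heavy drinkers. A shift in that uptake common to all regions gives 12%. The documents offer no basis for a change confined to the cerebellum. This largely stands, although the blocking result in heavy drinkers does not establish the same for controls.

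*The loss is neither certain nor total.* Stopping is optional, control arterial lines are the default, and seven healthy volunteers already have arterial V_T with this tracer (Section VI item 2, part c). So it would be wrong to say that the assumption could never be examined. But those volunteers had a mean age of 26, against eligibility of 21 to 65, and were not matched to the drinkers. They are a weak substitute for concurrent controls.

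The check is also imprecise, as the working shows. That limits how it may be used; it is not a reason to give up the data.

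**Conclusion.** The concern holds in a limited form. The planned validation supports the occupancy aims. It leaves untested the between-group assumption behind P3, and the plan as written could remove the concurrent control data that bear on it. The documents do not establish that a reference difference exists or that control arterial sampling will be dropped.

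For a 5% lower cerebellar value and no receptor difference, the false-positive rate runs from the nominal 5%, through about 12%, to about 62% (33% at BP_ND 1.0), depending on the mechanism. These figures rest on 56 versus 10 subjects and on assumed values for the shift, the 20% CV and, in the cerebellum-only case, BP_ND. The 62% should not be read as the expected error rate of P3.

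This is a cheap improvement to a primary aim. It does not undermine the occupancy aims.

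**What to change.** 1. In Analysis of Initial Cohort, state that any decision to stop arterial sampling does not apply to the controls' single scan.
2. Report the heavy-drinker versus control difference in cerebellar V_T with its 95% CI, from all baseline scans with arterial data.
3. Give P3 an analysis paragraph with BP_ND as its measure and regional V_T as a sensitivity analysis beside it. Reconcile the 10 and 25 controls there.
4. State the P3 conclusion as conditional on equal reference uptake, and show how much BP_ND bias the interval allows. For example, at a lower limit of −14%, a shift in all regions gives 1/0.86 − 1 = +16%; a cerebellum-only shift at BP_ND 0.5 gives 1.5/0.86 − 1 = 0.744, or +49%.

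Do not make a receptor conclusion depend on a non-significant V_T test or on V_T and BP_ND agreeing in direction. An interval of ±14% to ±18% cannot exclude a 5% shift. A true 20% BP_ND difference at 0.5 moves regional V_T only from 1.5 to 1.6 times the reference (6.7%), so the directions could differ by chance.

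The cost is protocol and SAP wording, plus arterial lines that continue in controls, with their burden and risk, even if dropped elsewhere. The V_T check remains imprecise.

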Ten minutes prior to the start of the priming dose (PD) period (i.e., 2:50 pm), the research assistant will walk into the participant's room with the glasses, the alcohol, and the mixers. The research assistant will then proceed with the mixing of the priming drink of alcohol in front of the participant. When done, he/she will leave the drink on the table, instruct the participant not to consume the priming drink until they are told to do so and leave the room.

Priming dose (PD) period

The PD of alcohol will be provided at 3 pm to model a "lapse" situation and subjects will have 5 minutes to drink it. A 40 minute absorption period will follow during which the alcohol craving (AUQ; [45]), stimulation/sedation (BAES; [46]) and physiological effects (heart rate, blood pressure, breath alcohol levels) of this priming dose of alcohol will be monitored every 10 minutes.

Alcohol self-administration (SA) periods

Following the PD, participants will be exposed to three one-hour SA periods designed to model a

“relapse” situation. During each SA period they will be permitted to drink up to four alcoholic drinks designed to raise Blood Alcohol Level (BAL) by 0.015 mg% of alcohol, or to receive cash (equivalent to the price of each drink that is not consumed). The first SA period will begin at 4 pm, when the research assistant will take 4 prepared drinks into the room along with a "tab" sheet worth \$12. The participant will be informed that these 4 drinks will be available to him/her for the next 60 minutes (i.e., until 5 pm). S/he can choose either to drink or to keep the money; each drink will cost \$3. For example, if the participant chooses to drink only one drink in the next one hour, s/he will earn \$9. The money will be given to them the next morning before they leave the hospital. The second and third SA periods will begin at 5 pm and 6 pm, respectively, and will be similar to the SA period. Thus, participants can choose to consume up to 12 additional drinks over this 3 hour period or to receive up to \$36 to take home the next morning. Number of drinks that each participant consumes during this period will serve as the primary outcome for this portion of the experiment.

❖ *Beverage content and mixers*

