- l) Psychophysiological Measures: These will include heart rate and blood pressure monitored

using a Critikon Dinamap while skin temperature will be measured using Yellow Springs Instruments 4600 precision thermometer. The cuff of the Dinamap will be on the subject's dominant arm while the probe of will be attached to the middle finger of the subject's non-dominant arm. These data will be further used to examine the safety of using the medication combination during alcohol self-administration.

1) **Cold Pressor Task** (Edens & Gil, 1995): To evaluate the ability of participants to deal with a physiological stressor and to examine pain thresholds in relation to medication effects and drinking behavior. Subjects will be informed that the experimenters are investigating the body's physiological response to cold water during nicotine withdrawal. Subjects will be asked to immerse their right arms into ice water maintained at 3-4°C. Subjects are asked to raise their left hand when they begin to feel pain (pain threshold) and to remove their hand from the water when they can no longer tolerate the pain (pain tolerance). While their hand is immersed in water subjects are also asked to rate their pain on an analog scale of 0-100.

3. **Statistical Considerations:** Describe the statistical analyses that support the study design. Outcomes for this study will be collected using scannable forms (Teleforms). The scanned forms will be processed through the Teleforms software and exported to a database on a secure computer. Error checking and data validation will occur weekly and any problems will be queried and resolved immediately. Drs. [name] will receive monthly data quality reports to check for completeness and accuracy of key demographic and prognostic variables, as well as rates of recruitment, retention, and follow-up. Statistical tests will be conducted using SAS v9.1 and SPSS v16 (or later) and will be performed at 2-tailed alpha level of 0.05

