Primary Aim 1. Occupancy of KOR by NTX and drinking. This aim seeks to determine the degree to which occupancy of kappa by NTX mediates responsivity to NTX in heavy drinkers. Responsivity to NTX is defined as the change in the total number of drinks consumed in the NTX ADP versus the baseline ADP. Tests for mediation will be conducted using the regression strategies described initially Baron and Kenny [53], and the more recent elaboration by Kraemer et al. [54]. The proposed mediator (i.e., the potential mechanism of change), occupancy of KORs, is measured as the fractional change in BP_{ND} before and after treatment with NTX. The analyses will determine whether occupancy is associated with a) NTX treatment, and b) NTX responsivity.

Primary Aim 2. Family History of Alcoholism as a moderator: This aim seeks to determine if the relationship between NTX responsivity and occupancy of KOR is altered by FH status. FHP and FHN will be compared on NTX responsivity and occupancy of KOR. Tests for moderation will be conducted using the strategies described by Baron and Kenny [53], and the elaborated by Kraemer et al. [54]. The primary tests will be whether there is a significant FH by dose interaction on NTX response and occupancy of KOR.

Secondary Aim 1. Baseline KOR differences. This aim seeks to determine if baseline levels of KOR differ between FHP and FHN heavy drinkers, and are related to either drinking in baseline or NTX ADP. FHP and FHN groups will be compared using chi-square tests for categorical variables, and using t-tests or Mann-Whitney tests for continuous variables. All continuous variables will be examined for adherence to the normal distribution using normal probability plots and Kolmogorov-Smirnov tests. If normality is not satisfied and transformations do not help with achieving normality, alternative analytic strategies will be considered such as generalized estimating equations or nonparametric methods. The relationship between baseline KOR and drinking will be examined via Pearson product-moment correlations.

Secondary Aims 2 and 3. Scan duration and reference region. We will look for correlations between BP_{ND} estimates based on 2T model with full AIF and all data vs alternative models and data ranges. Group variances in baseline KOR at or lower than 2T estimates will permit adoption of simpler models.

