The alcohol challenges will be conducted by personnel experienced in alcohol challenge research. As described above, all subjects will be under supervision to prevent possible accidents. At the end of the challenge session all subjects will be kept in the HRU where they will stay overnight to prevent the possibility that they would continue drinking after the session and place themselves at risk of accidents. Although we have never had a subject chose to leave a session early, should a subject insist on leaving the research setting prematurely, we will provide transportation back to their residence. This contingency is explicitly addressed in the consent form. Clearly, subjects are free to discontinue the experiment at any time. However, if a subject chose to discontinue participation after alcohol has been administered we will require them to stay in the HRU until their blood alcohol level is below 0.04 and they will then be provided with a ride home. Furthermore, at the Principal Investigator's discretion, a participant will be discontinued if he/she does not drink any of the choice drinks at ADP 1. This absence of drinking creates a floor effect and does not allow for evaluation of change in drinking behavior at ADP 2 after taking study medication. Given the cost of the scan and the hospital visit, it does not seem reasonable to continue participants whose data will not be meaningful. Participants will be told that the study doctor may discontinue his/her participation if they think you are not responding well to the medication.

3) Research Records:

Right to privacy for participation in this research will be protected through anonymous coding of data and proper storage of research records. Access will be limited to the PI and her designates involved in the study. A certificate of confidentiality has been obtained from NIAAA. Safeguards include screening by experienced professionals in order to ensure that the inclusion and exclusion criteria are met before patients are entered in the study, including physical exam and laboratory tests.

4) Risks Associated with Blood Drawing:

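### Primary Aim 1 relates KOR occupancy to a raw change in drinks and names no baseline-drinks covariate, giving up precision that data already collected could supply

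*Combined protocol and SAP*

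**What the plan says.** Specific Aims (P1) says that responsivity "is the change in number of drinks consumed at the baseline ADP vs. NTX ADP". Statistical Considerations, Primary Aim 1, repeats the definition: "Responsivity to NTX is defined as the change in the total number of drinks consumed in the NTX ADP versus the baseline ADP". The section on alcohol self-administration periods sets the range of each session: "participants can choose to consume up to 12 additional drinks over this 3 hour period". One session therefore gives 0 to 12 drinks, and the change can run from -12 to +12.

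Primary Aim 1 asks whether occupancy is associated with NTX treatment and with responsivity. It uses the Baron-Kenny regressions and a later elaboration of them, and lists no covariates. For Primary Aim 2, "FHP and FHN will be compared on NTX responsivity and occupancy of KOR". All tests "will be performed at 2-tailed alpha level of 0.05".

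Baseline drinks appear in two other places. Secondary Aim 1 relates baseline KOR to drinking in the sessions. Under Minimizing Risks (Alcohol Challenges), at the principal investigator's discretion, "a participant will be discontinued if he/she does not drink any of the choice drinks at ADP 1"; the reason given is a floor effect. The documents report no SD of session drinks and no correlation between the two sessions.

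**The concern.** A change score fixes the coefficient of baseline drinks at exactly 1. If session drinks vary from day to day, the best-fitting coefficient is usually below 1, and subtracting the whole baseline count adds its noise to the outcome. In a study of 36 to 56 heavy drinkers (the Specific Aims and power section use 18 per group; the Research Plan uses 56), that noise falls directly on the occupancy-responsivity test, which is the core of Primary Aim 1. Removing it needs no new data. The cited mediation methods would allow a baseline covariate, but the plan does not commit to one, so the choice would be made after the data are seen.

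**Working it through.** **The plan's own figure.** The power section gives 16 per arm for a family-history effect of .91 with 80% power. A two-sample t-test calculation gives 15.65, so 16, with one-sided alpha .05, and 19.96, so 20, with two-sided alpha. That mismatch is a separate matter. The figure concerns FHP versus FHN; the plan gives no power, SD or rho for the occupancy analysis, so everything below rests on stated assumptions.

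**Residual variance, equal session SDs (s).**
- Change score: s² + s² - 2·rho·s² = 2s²(1 - rho).
- Adjusted for baseline: s²(1 - rho²).
- Ratio: 2(1 - rho) / [(1 - rho)(1 + rho)] = 2/(1 + rho).

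| rho | 2/(1 + rho) | Extra variance of change score |
|---|---|---|
| 0.2 | 1.667 | 67% |
| 0.4 | 1.429 | 43% |
| 0.5 | 1.333 | 33% |
| 0.7 | 1.176 | 18% |
| 0.9 | 1.053 | 5% |

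**Unequal SDs.** With k = NTX SD / baseline SD, the ratio is (1 + k² - 2·rho·k) / [k²(1 - rho²)].
- k = 1.2, rho 0.8: (1 + 1.44 - 1.92)/(1.44 × 0.36) = 0.52/0.518 = 1.00, so no penalty. The best baseline coefficient, rho·k = 0.96, is already nearly 1.
- k = 1.2, rho 0.3: 1.72/1.310 = 1.31.
- k = 0.85, rho 0.8: 0.3625/0.2601 = 1.39.

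The ratio is never below 1, before the degree of freedom spent on the covariate.

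**Bounded counts.** Simulated scores rounded and clipped to 0-12 (assumed means 4 to 8, SDs 2.5 to 3.5, underlying rho 0.3 to 0.8) gave 8% to 71% extra variance, or 7% to 57% after removing those with no drinks at the first session.

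**Power for Primary Aim 1** (Fisher z, two-sided .05, occupancy unrelated to baseline drinks, equal SDs). Take n = 56 and an effect with 80% power on the change score.
- atanh(r) = (1.960 + 0.842)/√53 = 0.385, so r = 0.367 and r²/(1 - r²) = 0.1555.
- rho 0.4: 0.1555 × 1.429 = 0.222; partial r = √(0.222/1.222) = 0.426; atanh = 0.455; 0.455 × √52 - 1.960 = 1.32, or 91% power.
- rho 0.7: 0.1555 × 1.176 = 0.183; partial r = 0.393; the same steps give 85%.

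The same steps at n = 36 give about 85% to 90%. In simulation, for one illustrative effect at rho 0.4, power rose from 62% to 76% at n = 36 and from 81% to 92% at n = 56.

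**Why Primary Aim 2 differs.** Suppose NTX does nothing and one family-history group drinks g more in both sessions. The gap cancels in the change score, but the adjusted model reports a false effect of g(1 - rho). With SD 3 drinks:
- gap 0.5 SD, rho 0.7: 1.5 × 0.3 = 0.45 drinks;
- gap 0.8 SD, rho 0.4: 2.4 × 0.6 = 1.44 drinks.

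In simulations over these values, with 18 or 28 per group and scores clipped to 0-12, the change score rejected in 4% to 6% of runs and the adjusted model in 9% to 42%.

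**The case against.** The strongest reply is that the change score is a legitimate choice, and that the usual argument for baseline adjustment comes from randomised comparisons. Neither occupancy nor family history is randomised. For family history this stands: the calculation above shows that adjustment can create a difference where none exists. For occupancy it stands in part. If occupancy tracks a stable drinking trait, the adjusted slope is biased in the same way.

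The opposite case is equally possible. With no NTX effect and a predictor linked only to first-session drinks (assumed correlation 0.3 to 0.5, rho 0.4 to 0.7), the change score gave false positives in 10% to 36% of simulated trials at n = 36 and 12% to 51% at n = 56, against about 5% after adjustment. The documents do not show which structure applies, so both analyses should be reported.

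A second reply is that the bounds are already handled. The discontinuation rule addresses zeros, the upper limits on weekly drinking are meant to keep typical intake within the alcohol available, and Secondary Aim 1 offers transformations and nonparametric fallbacks. This is fair, and a linear covariate does nothing for the floor or ceiling anyway. None of it addresses the precision lost by subtraction.

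A reader might go further and infer that anything related to baseline drinking must correlate with responsivity even if NTX is inert, so that any KOR or family-history finding would be an artefact. The documents do not support that. A stable trait that shifts both sessions equally cancels, and the change-baseline correlation is not fixed: with equal SDs it is -0.55 at rho 0.4 and -0.39 at rho 0.7, but only -0.06 at rho 0.8 when the NTX SD is 1.2 times baseline. Nor is it right that baseline drinks serve only for subtraction, since Secondary Aim 1 analyses them directly.

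**Conclusion.** The point holds for Primary Aim 1 as an inexpensive gain in precision. It is not an error that invalidates the analysis. Under equal SDs and rho of 0.7 to 0.4, the change score carries 18% to 43% more residual variance; put the other way, adjustment removes 15% to 30% of the change-score variance, since (1 + rho)/2 is 0.85 to 0.70. An occupancy test with 80% power on the change score would then have about 85% to 91%, provided that occupancy is unrelated to baseline drinks. The direction is secure before the one degree of freedom is charged. The size is not, because the documents give neither rho nor the SDs, and with a larger NTX-session SD the gain can disappear. The point does not extend to replacing the change score in the family-history comparison of Primary Aim 2.

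**What to change.** - **Primary Aim 1:** regress NTX-ADP drinks on occupancy with baseline-ADP drinks as a covariate, and report the raw-change analysis beside it.
- **Primary Aim 2:** keep the change score for FHP versus FHN, report baseline drinks by family-history group, and show the baseline-adjusted result only as a sensitivity analysis. Say in advance that the two can disagree if the groups differ at baseline.
- **Inputs:** state the session SDs and rho from the preliminary ADP data, so that the expected gain can be judged.

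The cost is one degree of freedom and a few sentences in Statistical Considerations, with no added visits, scans or participants. The remaining risk is a biased adjusted estimate if occupancy tracks a stable drinking trait, which is why both Primary Aim 1 analyses should be shown. The 0 and 12 limits need separate comment, because adjustment does not remove them.
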